5.7.1.2 Pharmacodynamics

Pharmacodynamics are not evaluated in this study.

5.7.1.3 Genomics

Genomics is not evaluated in this study.

5.7.1.4 Immunological (Immunogenicity) Analysis

Immunogenicity variables are the anti-bimekizumab antibody status, anti-bimekizumab antibody titer and neutralizing anti-bimekizumab antibody status derived from anti-drug antibody assays. The analysis will be based on the SS.

Anti-bimekizumab antibodies will be measured using a 3-tiered assay approach: screening assay, confirmatory assay, and titration assay. Samples confirmed as positive within the confirmatory assay will be further evaluated. The samples will be titrated, and the ADA_b titer (reciprocal dilution factor, including the Minimum Required Dilution) will be reported. In addition, the sample will be assessed by a neutralizing antibody (NAb) assay to evaluate the potential of the ADA_b to neutralize the activity of bimekizumab (IL17A-specific or IL17F-specific, or both) in-vitro analysis details outlined in Section 5.7.1.4.2.

Samples were taken on the same schedule as PK assessments including Baseline, Week 1, Week 4, Week 8, Week 12, Week 16, Week 20, Week 40, Week 64, Week 88, Week 112, Week 124, EDV, and SFU.

Screening, confirmatory, and titer cut points of the respective assays will be determined by the bioanalytical laboratory based either on using commercially-available drug-naïve samples or on the predose samples obtained during the study.

Summary tables will be created for the Initial Treatment Period for all participants in the SS, and across the All Periods (Initial Treatment Period + OLE Period) summaries for all participants in the OLS.

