After the Screening Period of up to 5 weeks, eligible participants will be randomized to 1 of the 2 dose groups. The randomization will be stratified by weight category. During the Initial Treatment Period, participants will receive 5 doses of open-label bimekizumab (at Weeks 0 [Baseline], 4, 8, 12, and 16). Participants who complete the Initial Treatment Period, tolerate the treatment, and achieve an IGA response ≤ 2 at Week 20 may continue bimekizumab treatment at the same dose level in the OLE Period. All available study PK data and clinical data (including selected efficacy and safety data) starting from when 25% of participants have reached Week 16 will be assessed periodically until all participants have completed the Initial Treatment Period. The Phase 3 study (PS0021) dosing will be determined from this information. Upon identification of the PS0021 dose, study participants in PS0020 may switch to the PS0021 dose at the Investigator's discretion during the 104-week OLE Period. Participants who do not tolerate the IMP or who have an IGA response ≥ 3 (on a scale from 0 to 4) at Week 20 will be withdrawn from the study. Each participant will complete the SFU Period of 20 weeks following his/her final dose of bimekizumab (see study schematic in Section 1.2).

During the Initial Treatment Period, IMP will be administered by a health care professional at the study site. In the OLE Period, Dose A and Dose B may be administered at the study site or where possible at home. Home visits can be conducted during the OLE Period upon agreement of the Investigator, study participant, and his/her caregiver. Dose A of the IMP may be administered by a health care professional, caregiver, or study participant (once he/she becomes 18 years of age). Administration of Dose A by the caregiver or study participant is optional and requires training, as discussed in Section 6.2. Dose B will be administered by a health care professional, to ensure

accurate dosing of the lower volume of IMP. Planned IMP administration is described in the Schedule of Activities ([Table 1-1](#) and [Table 1-2](#)) and in Section 6.2.

The end of the study is defined as the date of the last participant's last visit. The study design of PS0020 provides participants who are receiving benefit from bimekizumab therapy with the opportunity to receive active treatment for a total of 120 weeks.

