9.1 Definition of analysis sets

The Enrolled Set (ES) will consist of all participants who have given informed consent/assent.

The Randomized Set (RS) will consist of all randomized participants. Unless otherwise stated, efficacy analyses will be based on the RS.

The Safety Set (SS) will consist of all participants that receive at least 1 dose of the IMP. Safety and immunogenicity analyses will be based on the SS.

The Pharmacokinetics Per-Protocol Set (PK-PPS) will consist of all randomized participants who receive at least 1 dose of the IMP and provide at least 1 quantifiable plasma concentration post-dose without important protocol deviations that would affect the concentration. Pharmacokinetic variables will be analyzed for all participants in the PK-PPS.

The Open-label Set (OLS) will consist of all study participants who receive at least 1 dose of IMP at or after Week 20 in the OLE Period (including the Week 20 dose).

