4.1.5 Open-label Set

The Open-label Set (OLS) will consist of all study participants who receive at least 1 dose of study medication at or after Week 20 in the OLE Period (including the Week 20 dose). The OLS will be the basis for analysis of data from OLE Period. OLS analyses will be based on the SS and as treated.

For summaries using both PK-PPS and OLS, participants will be summarized as randomized.

Immunogenicity analyses will be based on SS or OLS, and participants will be summarized as randomized.

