5.7.1.4.1 Anti-bimekizumab antibody

5.7.1.4.1.1 ADAAb sample status

The following definitions will be applied regarding ADAAb status of each test sample:

- An ADAAb status will be confirmed as positive for any sample that is positive screen and positive immunodepletion (regardless of availability of a titer value).
- An ADAAb status of negative will be concluded for any sample that is either negative screen, or positive screen and negative immunodepletion, and where the bimekizumab concentration is less than or equal to the drug tolerance limit (200 µg/mL) of the validated ADAAb assay.
- Inconclusive - sample that is either negative screen or positive screen and negative immunodepletion and where the bimekizumab concentration exceeds the validated ADAAb assay drug tolerance limit. These samples will be regarded as missing.

If the titer for a sample that is positive screen and positive immunodepletion is missing, then a conservative approach will be used and ADAAb status will be considered as positive. No imputation rules apply for the missing titer. If a sample is positive screen but no confirmatory result could be determined, then a conservative approach will be used and ADAAb status will be considered as positive.

5.7.1.4.1.2 Overall ADAAb status

A participant's overall ADAAb status will be derived by dose (320 mg, 160 mg, Total for Dose A, 64 mg, 32 mg, Total for Dose B, and Total for all participants). For participants who undergo dose modifications in the OLE, their data will be summarized by the dose assigned at Baseline. The following periods will be summarized:

- Overall ADAAb status to Week 16 (SS) : Including all visits (including and excluding Baseline) up to Week 16, excluding the SFU sample.
- Overall ADAAb status to Week 20 (SS) : Including all visits (excluding Baseline) up to Week 20, excluding and including the SFU sample. If $\geq 95\%$ of participants in the Initial Treatment Period enter the OLE Period, overall ADAAb status to Week 20 including the SFU sample will not be summarized.
- Overall ADAAb status to Week 124 (OLS): Including all visits up (excluding Baseline) to Week 124, excluding the SFU sample.
- Overall ADAAb status to SFU (OLS): Including all visits up (including and excluding Baseline) to SFU.

Over each of the periods defined above:

- Overall positive is defined as having at least one value that is confirmed positive (regardless of missing data).

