7. **Total treatment-emergent (category 7 [categories 2 and 5 combined]):** Includes study participants who are preADA b negative – treatment emergent ADA b positive (category 2) and preADA b positive – treatment boosted ADA b positive (category 5).
8. **Total prevalence of preADA b positivity (category 8 [categories 3, 4, 5, and 6 combined]):** Study participants that are tested ADA b positive at Baseline.
9. **Missing (category 9):** Includes participants who are antibody negative at Baseline and have more than 1 post-treatment scheduled assessments reported as missing/inconclusive, while other samples are ADA b negative. Note this is also applicable to participants who have a

missing Baseline sample, at least one missing/inconclusive postbaseline sample and have no ADAb positive samples.

Derivation for above classification will be different for the Initial Treatment Period (SS) and the combined Initial Treatment and OLE Periods (OLS). For the Initial Treatment Period, no OLE or SFU data will be considered. For the combined Initial Treatment and OLE Periods, data from the OLE and SFU visits be considered. That is, each instance of “excluding SFU” in the categories above, should be changed to “including SFU.”

In the case that a sample is collected 1 or more days following the scheduled visit date in which the drug was administered, the ADAb results for that sample will be associated with the scheduled visit and summarized accordingly. Such samples will also be considered when ADAb results are summarized over a given study period.

5.7.1.4.1.4 Cumulative ADAb status groups for PK summaries

The ADAb status (positive, negative or missing) will be considered in a cumulative manner at each time point for the PK summaries.

A study participant will be counted positive from the first visit at which the study participant achieved a positive ADAb sample result to the end of the treatment period, regardless of any missing/inconclusive or negative ADAb sample result.

If a study participant has only negative ADAb samples or only one missing/inconclusive sample with all negative ADAb samples up to that timepoint, the study participant will be classified as negative. An exception remains for the Baseline Visit where only one sample could be available. If the sample is missing/inconclusive, then the sample will be classified as being negative for the cumulative ADAb status.

Otherwise, the study participant will be classified in the missing ADAb category.

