6.2 Appendix 2: Changes to Protocol-Planned Analyses

The following have been added to the SAP, but are not present in the Protocol:

- The COVID-19 impact analysis (Section 5.2.1) has been added.
- The definition of analysis sets has been changed (Section 4.1):
 - Immunogenicity analyses will be based on SS or OLS, and participants will be summarized as randomized.
 - Pharmacokinetic variables will be analyzed for all participants in the PK-PPS and will be summarized as randomized.
 - OLS analyses will be based on the SS and as treated.
 - For summaries using both PK-PPS and OLS, participants will be summarized as randomized.
- Multiple imputation is no longer being applied to missing continuous data. Instead, the LOCF method will be used to impute the missing value (Section 5.1.1.7.3).
- Shift tables for growth assessments for height and weight (Section 5.6.3.6.2) have been added.

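### Combined-period ADAb status and subcategory tables use only participants who entered the OLE, so a non-entrant's Safety Follow-up sample never counts toward treatment-emergent incidence

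*SAP*

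**What the plan says.** Protocol 9.1 is unconditional: "Safety and immunogenicity analyses will be based on the SS". Protocol 9.4.2 repeats the SS for antibody levels. SAP 5.7.1.4 opens in agreement ("The analysis will be based on the SS"). Its closing sentence then puts the Initial Treatment Period tables on the SS and the remainder "across the All Periods (Initial Treatment Period + OLE Period) summaries for all participants in the OLS". SAP 6.2 lists the change from the protocol without giving a reason: "Immunogenicity analyses will be based on SS or OLS, and participants will be summarized as randomized".

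The OLS contains participants "who receive at least 1 dose of study medication at or after Week 20 in the OLE Period" (SAP 4.1.5). To receive that dose a participant must have completed the Initial Treatment Period, tolerated the drug and reached an IGA of 2 or less. Under Protocol 4.1, those who do not tolerate it or have an IGA of 3 or more "at Week 20 will be withdrawn from the study".

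SAP 5.7.1.4.1.2 labels overall ADAb status to Week 124 and to SFU as OLS. It plans overall status to Week 20 on the SS, with and without the SFU sample, but the version with SFU is not produced if at least 95% "of participants in the Initial Treatment Period enter the OLE Period". SAP 5.7.1.4.1.3 derives the subcategories once per period: "For the Initial Treatment Period, no OLE or SFU data will be considered", while the combined-period version uses OLE and SFU data but only in the OLS.

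**The concern.** The secondary objective is immunogenicity in adolescents with moderate to severe plaque psoriasis, not in those who did well to Week 20. Response and tolerability are post-baseline outcomes that antibodies could affect, so a set selected on them may not show the antibody rate of the treated population.

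There is also a gap in sample use. Protocol Table 1-1 schedules an antibody sample at SFU, and Protocol 8.9.1 asks for a final-visit sample from participants who discontinue or withdraw. For a participant who never enters the OLE, that sample has almost nowhere to go. Safety is handled differently: SAP 5.6 allows combined-period safety summaries on the SS, and SAP 5.6.2.1 sends late adverse events that fall outside the Initial Treatment Period output into the combined summaries. Antibody status has no equivalent route.

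**Working it through.** The documents give no expected ADAb rate, so there is no planned figure to reproduce. The check has four parts.

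**1. Where a non-entrant's samples go**

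| Output | Set | Samples to Week 20 | SFU sample |
|---|---|---|---|
| Overall status to Week 16; to Week 20 without SFU | SS | used | not used |
| Overall status to Week 20 with SFU | SS | used | used, unless the 95% rule cancels the table |
| Overall status to Week 124; to SFU | OLS | participant excluded | participant excluded |
| Subcategories, Initial Treatment Period | SS | used | not used |
| Subcategories, combined periods | OLS | participant excluded | participant excluded |

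Category 7 comes from the subcategory tables, so a non-entrant's SFU sample never reaches it, whatever the 95% rule gives. A non-entrant who is negative at Baseline and through Week 20 but positive at SFU is reported as category 1, treatment-emergent negative.

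**2. Reach of the 95% rule**

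Take N = 40 (SAP 3: at least 40, 1:1, so 20 per arm) and k non-entrants. The rule is met when (40 − k)/40 ≥ 0.95. For k = 2, 38/40 = 95.0%, met; for k = 3, 37/40 = 92.5%, not met. At most 2 participants are affected. If both are positive only at SFU, overall positivity moves by 2/40 = 5 percentage points, or 2/20 = 10 points if both are in one arm. For assumed true entry probabilities of 85%, 90%, 95% and 97%, the binomial chance that 38 or more of 40 enter is 4.9%, 22.3%, 67.7% and 88.2%.

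**3. Effect of the OLS restriction**

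Let pO and pN be the ADAb-positive rates in entrants and non-entrants. Then

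SS rate − OLS rate = (k/N)(pN − pO).

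The rates below are assumptions; N = 40.

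| k | pO | pN | OLS rate | SS rate | Difference (points) |
|---|---|---|---|---|---|
| 2 | 30% | 60% | 30.0% | 31.5% | 1.5 |
| 4 | 30% | 60% | 30.0% | 33.0% | 3.0 |
| 8 | 30% | 60% | 30.0% | 36.0% | 6.0 |
| 2 | 30% | 100% | 30.0% | 33.5% | 3.5 |
| 8 | 30% | 100% | 30.0% | 44.0% | 14.0 |
| any | 30% | 30% | 30.0% | 30.0% | 0 |
| 4 | 30% | 10% | 30.0% | 28.0% | −2.0 |

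The last row is (4/40)(10 − 30) = −2.0. The sign follows pN − pO, which the documents do not give. Unlike the 95% rule, this difference has no cap at 2 participants.

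**4. What happens if only the set is changed**

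Under SAP 5.7.1.4.1.2, a participant with more than one missing sample, including a missed scheduled collection, and otherwise negative results is classed as missing. Category 9 works in the same way. A non-entrant run to Week 124 or SFU on the SS would lack Weeks 40, 64, 88, 112 and 124, which is five samples. That participant could be only positive or missing, never negative. Removing negatives but keeping positives would create a new distortion.

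**The case against.** A reader might infer that the removed participants' antibody data disappear from the report. They do not. Samples through Week 20 stay in the SS tables: six post-baseline visits (Weeks 1, 4, 8, 12, 16 and 20), covering the whole dosing period of a non-entrant. SAP 5.1.1.1.4 maps early-discontinuation ADAb samples to the next ADAb visit so that they count. SAP 5.7.1.4.1.6 lists all individual results and plots titers for all participants over the full study, with SFU included at the final analysis. If 4 of 40 stay out, entry is 90%, the 95% rule is not triggered, and the SS table to Week 20 with SFU is produced.

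A reader might also infer that every full-study antibody output is confined to the OLS. SAP 5.7.1.4.1.6 says analyses are run on both SS and OLS unless specified otherwise; the first-occurrence table there carries no OLS label, and the NAb table in SAP 5.7.1.4.2.1 names no set. The text is inconsistent on these outputs rather than restrictive. The explicit OLS labels on overall status and subcategories do specify otherwise, so the general sentence does not rescue them.

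Finally, the choice is disclosed, the study is descriptive, and reporting on-drug incidence in the SS and long-term incidence in those who continue is coherent. SAP 5.6 expects only a few non-entrants. This supports keeping the OLS tables. It does not explain why category 7 should ignore SFU samples from treated participants, and few non-entrants means an SS version costs little.

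**Conclusion.** The point holds as a gap in the tables. Overall ADAb status to Week 124 and to SFU, and the combined-period subcategories, are produced only in a set selected on completion, tolerability and Week 20 IGA, contrary to Protocol 9.1 and the opening of SAP 5.7.1.4. A non-entrant's SFU sample never counts toward category 7. It counts toward overall status only in a table that may be cancelled, at a cost of at most 5 points overall or 10 points in one arm when N = 40.

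It is tempting to conclude that study-wide incidence is biased downward, and more so at the lower dose. The documents do not support that: they give no ADAb rate by OLE entry and no expected entry rate by dose, and non-entrants have shorter exposure and fewer samples, which could pull their rate either way. Understatement follows only if non-entrants are ADAb positive more often. This is a cheap improvement to a secondary descriptive analysis.

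**What to change.** In SAP 5.7.1.4, 5.7.1.4.1.2 and 5.7.1.4.1.3:

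- Add SS versions of the combined-period overall-status table (to SFU) and the subcategory table, including category 7. Use every post-baseline sample, including the SFU sample of participants who never entered the OLE.
- For these tables, count as missing only samples scheduled up to the participant's last expected study visit, SFU included, so that a non-entrant with negative results can be classed as negative.
- Delete the 95% suppression rule for overall status to Week 20 including SFU.
- Keep the OLS versions as supportive.
- State the analysis set for the NAb table (5.7.1.4.2.1) and the first-occurrence table (5.7.1.4.1.6), and reconcile the statements on analysis set in 5.7.1.4, 5.7.1.4.1.3 and 5.7.1.4.1.6.

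The cost is SAP wording, one derivation rule and a few more tables; the samples are already in the schedule. The downside is uneven follow-up within the SS, since non-entrants contribute about 20 weeks plus SFU and entrants up to 124 weeks plus SFU. A footnote giving the number of non-entrants per arm would let readers judge this.

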5.7.1.4.1 Anti-bimekizumab antibody

5.7.1.4.1.1 ADAAb sample status

The following definitions will be applied regarding ADAAb status of each test sample:

- An ADAAb status will be confirmed as positive for any sample that is positive screen and positive immunodepletion (regardless of availability of a titer value).
- An ADAAb status of negative will be concluded for any sample that is either negative screen, or positive screen and negative immunodepletion, and where the bimekizumab concentration is less than or equal to the drug tolerance limit (200 µg/mL) of the validated ADAAb assay.
- Inconclusive - sample that is either negative screen or positive screen and negative immunodepletion and where the bimekizumab concentration exceeds the validated ADAAb assay drug tolerance limit. These samples will be regarded as missing.

If the titer for a sample that is positive screen and positive immunodepletion is missing, then a conservative approach will be used and ADAAb status will be considered as positive. No imputation rules apply for the missing titer. If a sample is positive screen but no confirmatory result could be determined, then a conservative approach will be used and ADAAb status will be considered as positive.

5.7.1.4.1.2 Overall ADAAb status

A participant's overall ADAAb status will be derived by dose (320 mg, 160 mg, Total for Dose A, 64 mg, 32 mg, Total for Dose B, and Total for all participants). For participants who undergo dose modifications in the OLE, their data will be summarized by the dose assigned at Baseline. The following periods will be summarized:

- Overall ADAAb status to Week 16 (SS) : Including all visits (including and excluding Baseline) up to Week 16, excluding the SFU sample.
- Overall ADAAb status to Week 20 (SS) : Including all visits (excluding Baseline) up to Week 20, excluding and including the SFU sample. If $\geq 95\%$ of participants in the Initial Treatment Period enter the OLE Period, overall ADAAb status to Week 20 including the SFU sample will not be summarized.
- Overall ADAAb status to Week 124 (OLS): Including all visits up (excluding Baseline) to Week 124, excluding the SFU sample.
- Overall ADAAb status to SFU (OLS): Including all visits up (including and excluding Baseline) to SFU.

Over each of the periods defined above:

- Overall positive is defined as having at least one value that is confirmed positive (regardless of missing data).

- Overall negative, if the study participant has all samples reported as negative or has only one missing/inconclusive sample.
- Overall missing, if the study participant has more than one missing ADA b sample for any reason (eg, insufficient sample, ADA b sample status is inconclusive, no result is available or a missed scheduled collection) and all other available ADA b samples are negative.

5.7.1.4.1.3 ADA b Subcategories

Furthermore, the following subcategories for each participant will be derived:

1. **Pre ADA b negative – treatment-emergent ADA b negative (category 1):** Includes participants who are negative at Baseline and ADA b negative at all sampling points posttreatment (excluding SFU) or has only one postbaseline missing/inconclusive sample. This includes study participants who have a missing/inconclusive sample at Baseline with all post-treatment samples reported as ADA b negative.
2. **Pre ADA b negative – treatment-emergent ADA b positive (category 2):** Includes participants who are negative at Baseline and ADA b positive at any sampling point posttreatment (excluding SFU). This group also includes participants who have a missing/inconclusive sample (either missing or insufficient volume) at Baseline with 1 or more ADA b positive posttreatment samples.
3. **Pre ADA b positive – treatment-emergent reduced ADA b (category 3):** Includes participants who are positive at Baseline, and ADA b negative at all sampling points posttreatment (excluding SFU) or has only one post-Baseline missing/inconclusive sample.
4. **Pre ADA b positive – treatment-emergent unaffected ADA b positive (category 4):** Includes participants who are positive at Baseline and are positive at any sampling point posttreatment (excluding SFU) with titer values of the same magnitude as Baseline (ie, < 2.07-fold difference from the Baseline value; 2.07 being the validated minimum significant ratio for this assay method).
5. **Pre ADA b positive – treatment-emergent ADA b boosted positive (category 5):** Includes participants who are positive at Baseline and are positive at any sampling point post treatment (excluding SFU) with increased titer values compared to Baseline (≥ 2.07 -fold difference increase from Baseline).
6. **Inconclusive (category 6):** Includes participants who have a positive Baseline sample, and some posttreatment samples are missing/inconclusive, while other posttreatment samples are ADA b negative.
7. **Total treatment-emergent (category 7 [categories 2 and 5 combined]):** Includes study participants who are preADA b negative – treatment emergent ADA b positive (category 2) and preADA b positive – treatment boosted ADA b positive (category 5).
8. **Total prevalence of preADA b positivity (category 8 [categories 3, 4, 5, and 6 combined]):** Study participants that are tested ADA b positive at Baseline.
9. **Missing (category 9):** Includes participants who are antibody negative at Baseline and have more than 1 post-treatment scheduled assessments reported as missing/inconclusive, while other samples are ADA b negative. Note this is also applicable to participants who have a

missing Baseline sample, at least one missing/inconclusive postbaseline sample and have no ADAb positive samples.

Derivation for above classification will be different for the Initial Treatment Period (SS) and the combined Initial Treatment and OLE Periods (OLS). For the Initial Treatment Period, no OLE or SFU data will be considered. For the combined Initial Treatment and OLE Periods, data from the OLE and SFU visits be considered. That is, each instance of “excluding SFU” in the categories above, should be changed to “including SFU.”

In the case that a sample is collected 1 or more days following the scheduled visit date in which the drug was administered, the ADAb results for that sample will be associated with the scheduled visit and summarized accordingly. Such samples will also be considered when ADAb results are summarized over a given study period.

5.7.1.4.1.4 Cumulative ADAb status groups for PK summaries

The ADAb status (positive, negative or missing) will be considered in a cumulative manner at each time point for the PK summaries.

A study participant will be counted positive from the first visit at which the study participant achieved a positive ADAb sample result to the end of the treatment period, regardless of any missing/inconclusive or negative ADAb sample result.

If a study participant has only negative ADAb samples or only one missing/inconclusive sample with all negative ADAb samples up to that timepoint, the study participant will be classified as negative. An exception remains for the Baseline Visit where only one sample could be available. If the sample is missing/inconclusive, then the sample will be classified as being negative for the cumulative ADAb status.

Otherwise, the study participant will be classified in the missing ADAb category.

5.7.1.4.1.5 ADAb status groups for Efficacy Endpoint Summaries

For purposes of efficacy subgroup analyses based on ADAb status, 3 categories will be used:

- ADAb positive – Defined as participants who have at least 2 ADAb positive samples up to the time point of interest (ie, excluding Baseline) regardless of other ADAb samples and/or missing or inconclusive samples.
- ADAb negative – Defined as study participants for whom either (1) all samples to the timepoint of interest are ADAb negative and there are no missing or inconclusive samples, (2) only 1 post-Baseline sample is ADAb positive and all others to the timepoint of interest are ADAb negative or missing/inconclusive or (3) only one sample is missing/inconclusive and the remaining ADAb samples are negative.
- Missing – Defined as study participants who do not fulfil the criteria for one of the 2 groups listed above.

ADAb status for efficacy subgroups will be derived at Week 16 (excluding SFU) for the Initial Treatment Period and Week 124 (including SFU) for the combined Initial Treatment and OLE Periods (OLS).

5.7.1.4.1.6 Analysis

Immunogenicity will be assessed through summary tables, figures, and listings of individual results by participant. Analyses will be run on the SS and OLS, unless specified otherwise. All individual participant-level ADA_b results will be listed. The listing will also include flags and reasons for exclusion for ADA_b measurements that were excluded from the by-visit summaries (as detailed below), as well as information on whether the BKZ concentration exceeds the ADA_b assay drug tolerance limit.

In the case that a ADA_b sample is collected within ± 21 days relative to the visit date at which BKZ was administered (or ± 21 days from a scheduled visit at which BKZ dosing was not planned eg, ET or SFU visits), the ADA_b result for that sample will be associated with the scheduled visit and summarized accordingly. Samples collected outside of this window will be excluded from the ADA_b by-visit summaries and will be listed only. All other summaries of ADA_b status (Section 5.7.1.4.1.2 to Section 5.7.1.4.1.5) will use all available (scheduled and unscheduled visit) data. Tables and figures listed below will be summarized by dose (320 mg, 160 mg, Total for Dose A, 64 mg, 32 mg, Total for Dose B, and Total for all participants). For participants who switch dose during the OLE, their data will be summarized by weight-categorized dose group at Baseline.

- Summary of ADA_b status overall and by each visit will be presented over the periods of interest (Section 5.7.1.4.1.2). This includes overall ADA_b status for the efficacy endpoint summaries (Section 5.7.1.4.1.5).
- Number and percentage of study participants with first occurrence of ADA_b positive result (on an ordinary and cumulative basis) by visit, for any ADA_b positive and Total treatment-emergent ADA_b positive (category 7 [categories 2 and 5 combined]) results over the study duration will be presented. Box-plots of the titer by time to first ADA_b positivity will be prepared.
- The number and percentage of participants in each of the 9 ADA_b subcategories (Section 5.7.1.4.1.3) over the study duration.
- Figure of PASI90 responders (based on NRI), separated by dose group (BKZ Dose A and BKZ Dose B), at Week 16 and Week 124 as a function of ADA_b titer group (categorized as ADA_b negative, titer < 100, and titer tertiles ≥ 100), will be presented graphically. If not supported by the data, the titer tertile groupings may be reduced eg ≥ 100 - <median [of the non-missing titer values ≥ 100], and ≥ 100 median [of the non-missing titer values ≥ 100]]. This will be repeated for IGA 0/1 (based on NRI).
- The number and percentage of PASI90 responders versus time for each dose group (BKZ Dose A and BKZ Dose B) will be summarized by overall ADA_b status (Section 5.7.1.4.1.5, ADA_b negative, ADA_b positive, missing). If $\geq 95\%$ of subjects are included in the non-missing ADA_b groups, the missing group will not be displayed in the figure. The data will be presented in a tabular (based on NRI and OC) and graphical (based on NRI only) format. The analyses will be repeated for IGA0/1.
- Individual plots of bimekizumab concentrations / ADA_b titer and PASI90 response (based on NRI) will be created. All three endpoints will be plotted on the Y-axes by visit (x-axis) for all participants for the full study duration. For interim analyses, the SFU visit and OLE period

will be excluded and for the final analyses, the SFU visit and OLE period will be included. Plots should be labeled and grouped into the 7 primary subcategories (excludes category 7 and category 8).

- Spaghetti plots of ADA_b titer (y-axis) by visit (x-axis), separated by weight-categorized dose group for all ADA_b positive participants in category 2 and category 5, may be provided.

Treatment emergent adverse events will be summarized by ADA_b status using the following categories:

- AEs starting before first ADA_b positive result
- AEs starting on or after first ADA_b positive result
- AEs for participants who were always ADA_b negative

A study participant's associated time at risk will be split into the time before the first positive result and on or after the first positive result. If a study participant has multiple reports of the same AE (ie, those which code to the same preferred term) emerging both prior to first ADA_b positive result and after ADA_b positive result, both events will be summarized in the table in the appropriate column.

